Subjects who discontinue preladenant in monotherapy (Arm 1) due to progressive disease may, at the investigator's discretion and after consultation with the Sponsor, cross-over to the combination treatment (Arm 2) (see Sections 4.2.3.1 and 4.2.3.2). It will be at the discretion of the investigator whether to continue a subject on study treatment until repeat imaging is obtained. Once they discontinue from any part of the study, subjects will be treated at the discretion of the physician.

After treatment discontinuation, subjects will be monitored for AEs and SAEs for 90 days. Subjects who initiate new anticancer therapy less than 30 days after study treatment discontinuation will be monitored for AEs/SAEs for 30 days. Subjects who initiate new anticancer therapy between 30 days and 90 days after study treatment discontinuation will be monitored for AEs/SAEs until the day new anticancer therapy is initiated.

Subjects with an ongoing AE of Grade >1 at the time of treatment discontinuation will be followed until resolution of the AE to Grade 0-1, until considered stable by the treating physician, or until beginning a new anti-cancer therapy, whichever occurs first.

Subjects who discontinue treatment for reasons other than confirmed progressive disease will have post-treatment follow-up for disease status (including imaging) until progressive disease, initiating a new anti-cancer therapy, discontinuing from the study participation, or becoming lost to follow-up.

[figure not shown]
After confirmed progressive disease each subject will be contacted by telephone every 12 weeks (84±7 days) for survival until subject discontinues from the study, becoming lost to follow-up, death, or end of the study, whichever occurs first.

The trial will be conducted in conformance with Good Clinical Practices (GCP).

Specific procedures to be performed during the trial, as well as their prescribed times and associated visit windows, are outlined in the Trial Flow Chart - Section 6.0. Details of each procedure are provided in Section 7.0 – Trial Procedures.

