9. Adverse events and serious adverse events will be recorded from the time of treatment allocation. All adverse events and serious adverse events that occur after the consent form is signed but before treatment allocation must be reported by the Investigator if they cause the subject to be excluded from the trial, or are the result of a protocol-specified intervention, including but not limited to washout or discontinuation of usual therapy or a study procedure. After treatment discontinuation, each subject will be followed for 90 days for adverse event and serious adverse event monitoring, 30 days if the subject initiates new anticancer therapy less than 30 days after study treatment discontinuation, or the day new anticancer therapy is initiated if between 30 days and 90 days after study treatment discontinuation. Subjects with an ongoing AE of Grade >1 at the time of treatment discontinuation will be followed until resolution of the AE to Grade 0-1, until considered stable by the treating physician, or until beginning a new anticancer therapy, whichever occurs first.
10. Baseline radiology images by CT (or MRI) of chest, abdomen, and pelvis, and all known tumor sites (if evaluable by imaging) must be obtained within 28 days prior to C1D1 and must be repeated every 9 weeks ( $\pm 7$  days) from C1D1 (See SIM). Imaging must be obtained at the End of Treatment visit at discontinuation unless done within the previous 4 weeks. Images are to be submitted to the central imaging vendor for potential future central analysis.
11. After confirmed disease progression subjects will be contacted by telephone every 12 weeks for survival until withdrawal of consent to participate in the study, becoming lost to follow-up, death, or end of the study, whichever occurs first.
12. Tumor tissue (archival or newly obtained biopsy) will be required at Screening upon signing the informed consent for the study. This sample will be assessed to collect information on biomarkers for all subjects enrolled in the study. Tumor tissue will be sent to central laboratory for biomarker analysis and leftover tissue may be saved for future biomedical research (FBR) if the subject signs the FBR consent.

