10. Adverse events and serious adverse events will be recorded from the time of treatment allocation. All adverse events and serious adverse events that occur after the consent form is signed but before treatment allocation must be reported by the Investigator if they cause the subject to be excluded from the trial, or are the result of a protocol-specified intervention, including but not limited to washout or discontinuation of usual therapy or a study procedure. After treatment discontinuation, each subject will be followed for 90 days for adverse event and serious adverse event monitoring, 30 days if the subject initiates new anticancer therapy less than 30 days after study treatment discontinuation, or the day new anticancer therapy is initiated if between 30 days and 90 days after study treatment discontinuation. Subjects with an ongoing AE of Grade >1 at the time of treatment discontinuation will be followed until resolution of the AE to Grade 0-1, until considered stable by the treating physician, or until beginning a new anticancer therapy, whichever occurs first.
11. Baseline radiology images by CT (or MRI) of chest, abdomen, and pelvis, and all known tumor sites (if evaluable by imaging) must be obtained within 28 days prior to C1D1 and must be repeated every 9 weeks ( $\pm 7$  days) from C1D1. Confirmatory imaging are required for all responses (CR and PR) seen by imaging at the study site should be obtained at least 4-5 weeks after the documented response. Imaging must be obtained at the End of Treatment visit at discontinuation unless done within the previous 4 weeks. Images are to be submitted to the central imaging vendor for potential future central analysis.
12. After confirmed disease progression subjects will be contacted by telephone every 12 weeks for survival until withdrawal of consent to participate in the study, becoming lost to follow-up, death, or end of the study, whichever occurs first.
13. Tumor tissue (archival or newly obtained biopsy) will be required at Screening upon signing the informed consent for the study. This sample will be assessed to collect information on biomarkers for all subjects enrolled in the study. Tumor tissue will be sent to central laboratory for biomarker analysis and leftover tissue may be saved for future biomedical research (FBR) if the subject signs the FBR consent.

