#### **7.1.2.6.3 End of Treatment and Follow-up Treatment Imaging**

In subjects who discontinue trial treatment, tumor imaging should be performed at the time of treatment discontinuation ( $\pm$ 4-week window). If a previous scan was obtained within 4 weeks prior to the date of discontinuation, then a scan at treatment discontinuation is not mandatory. In subjects who discontinue trial treatment due to documented disease progression, this is the final required tumor imaging.

In subjects who discontinue trial treatment without documented disease progression, every effort should be made to continue monitoring their disease status by tumor imaging using the same imaging schedule used while on treatment (every 9 weeks) to monitor disease status

until the start of a new anticancer treatment, disease progression, death, or the end of the trial, whichever occurs first.

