#### **7.1.2.6.5 irRECIST Assessment of Disease**

irRECIST is RECIST 1.1 adapted as described below to account for the unique tumor response seen with immunotherapeutic drugs. irRECIST will be used by the site Investigator/local radiology reviewers to assess tumor response and progression, and make treatment decisions. This data will be collected in the clinical database.

When feasible, subjects should not be discontinued until progression is confirmed by the local site Investigator/radiology assessment. This allowance to continue treatment despite initial radiologic PD takes into account the observation that some subjects can have a transient tumor flare in the first few months after the start of immunotherapy, and then experience subsequent disease response. Subjects that are deemed clinically unstable are not required to have repeat tumor imaging for confirmation of PD. Tumor flare includes any of the following scenarios:

- Worsening of existing target lesion(s)
- Worsening of existing nontarget lesion(s)
- Development of new lesion(s)

In subjects who have shown initial evidence of radiological PD by RECIST 1.1, it is at the discretion of the Investigator whether to continue a subject on trial medication until repeat imaging is obtained (using irRECIST for subject management (see [Table 12](#)). This clinical judgment decision by the site Investigator should be based on the subject's overall clinical condition, including performance status, clinical symptoms, and laboratory data. Subjects may receive trial medication and the tumor assessment should be repeated  $\geq 4$  weeks later in order to confirm PD by irRECIST per site assessment. Clinical stability is defined as the following:

- Absence of symptoms and signs indicating clinically significant progression of disease, including worsening of laboratory values
- No decline in ECOG performance status
- Absence of rapid progression of disease
- Absence of progressive tumor at critical anatomical sites (e.g., cord compression) requiring urgent alternative medical intervention

Any subject deemed clinically unstable should be discontinued from trial treatment at site-assessed first radiologic evidence of PD and is not required to have repeat imaging for PD confirmation.

In determining whether or not the tumor burden has increased or decreased per irRECIST, the local site Investigator should consider all target and non-target lesions, as well as any incremental new lesion(s).

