#### **7.1.5.3.4 Survival Follow-up Visits**

Subjects, who experience confirmed disease progression or start a new anti-cancer therapy, will move into the Survival Follow-Up Phase and should be contacted by telephone every 12 weeks to assess for survival status until death, withdrawal of consent, or the end of the study, whichever occurs first.

The Sponsor may request survival status be assessed at additional time points during the course of the study. For example, these additional time points may be requested prior to an efficacy interim analysis, and/or final analysis. All subjects who are not known to have died prior to the request for these additional survival status time points will be contacted at that time.

When a subject discontinues trial treatment in treatment period and/or retreatment period, procedures for discontinuation will be conducted.

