### **7.2.3 Immediate Reporting of Adverse Events to the Sponsor**

#### **7.2.3.1 Serious Adverse Events**

A serious adverse event is any adverse event occurring at any dose or during any use of Sponsor's product that:

- Results in death;
- Is life threatening;
- Results in persistent or significant disability/incapacity;
- Results in or prolongs an existing inpatient hospitalization;
- Is a congenital anomaly/birth defect;
- Is an other important medical event.

**Note:** In addition to the above criteria, adverse events meeting either of the below criteria, although not serious per ICH definition, are reportable to the Sponsor in the same timeframe as SAEs to meet certain local requirements. Therefore, these events are considered serious by the Sponsor for collection purposes.

- Is a new cancer (that is not a condition of the study);
- Is associated with an overdose.

Refer to [Table 14](#) for additional details regarding each of the above criteria.

For the time period beginning when the consent form is signed until treatment allocation/randomization, any serious adverse event, or follow up to a serious adverse event, including death due to any cause other than progression of the cancer under study (reference Section 7.2.3.3 for additional details), that occurs to any subject must be reported within 24 hours to the Sponsor if it causes the subject to be excluded from the trial, or is the result of a protocol-specified intervention, including but not limited to washout or discontinuation of usual therapy, diet, placebo treatment or a procedure.

For the time period beginning at treatment allocation/randomization through 90 days following cessation of trial treatment, or 30 days following cessation of trial treatment if the subject initiates new anticancer therapy, whichever is earlier, any serious adverse event, or follow up to a serious adverse event, including death due to any cause other than progression of the cancer under study (reference Section 7.2.3.3 for additional details), whether or not related to the Sponsor's product, must be reported within 24 hours to the Sponsor either by electronic media or paper. Electronic reporting procedures can be found in the EDC data entry guidelines. Paper reporting procedures can be found in the Investigator Trial File Binder (or equivalent).

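### Survival follow-up has three different entry rules, and under the text triggers a clinically unstable subject stopped at unconfirmed progression has no scheduled route into it; exploratory OS may be biased upward

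*Combined protocol and SAP*

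**What the plan says.** Entry to survival follow-up is described in five places.

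- Section 2.1: "After confirmed progressive disease each subject will be contacted by telephone every 12 weeks (84±7 days) for survival".
- Section 6.1, Arm 2 footnote 12, with Arm 1 footnote 11 identical: "After confirmed disease progression subjects will be contacted by telephone every 12 weeks for survival".
- The column that those footnotes annotate times the 12-weekly contact from treatment discontinuation and does not mention confirmation.
- Section 7.1.5.3.4: "Subjects, who experience confirmed disease progression or start a new anti-cancer therapy, will move into the Survival Follow-Up Phase". It adds that the Sponsor may ask for extra survival checks, which would reach everyone not known to have died.
- Section 7.1.1.6.2 also sends a subject who starts another anticancer therapy into survival follow-up.

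For a clinically unstable subject, Section 7.1.2.6.5 stops treatment at the first radiologic PD, and the subject "is not required to have repeat imaging for PD confirmation". Table 12 leaves a repeat scan to the physician's discretion. The same section treats progression as confirmed when two scans at least 4 weeks apart show it.

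On imaging after stopping, Section 7.1.2.6.3 says "In subjects who discontinue trial treatment due to documented disease progression, this is the final required tumor imaging". Section 7.1.5.3.3 continues imaging after a stop for anything other than verified PD until PD is verified or confirmed, or until new therapy, death, withdrawal of consent or study end.

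SAE reporting covers deaths "including death due to any cause other than progression of the cancer under study" (7.2.3.1). OS is an exploratory objective (3.3). Section 8.4.1 leaves the definitions of endpoints other than ORR to the supplemental SAP.

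**The concern.** Clinical instability, as Section 7.1.2.6.5 describes it, means symptoms of progression, declining ECOG status, rapid progression or tumour at a critical site. Subjects stopped for that reason can be expected to die sooner than other progressors. If the follow-up rule loses them because their PD was never confirmed, they are censored for a reason tied to prognosis. Kaplan-Meier estimation assumes that censored subjects have the same later risk as those still observed. If that fails in this direction, the OS curve sits too high.

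At stake are the OS summaries for each regimen and any informal reading of them when later trials are planned. A death date not collected during the trial may be hard to recover afterwards. The conflicting rules also leave sites to choose between them, so follow-up may differ by site.

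**Working it through.** **Step 1. Apply each rule to two subjects.** Subject U is clinically unstable, is stopped at first PD, has no repeat scan and starts no new therapy. Subject T stops for toxicity and starts new therapy before PD.

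| Place | Entry condition | U enters? | T enters? |
|---|---|---|---|
| 2.1 | confirmed PD | no | no |
| 6.1 footnotes 11, 12 | confirmed PD | no | no |
| 7.1.5.3.4 | confirmed PD or new therapy | no | yes |
| 7.1.1.6.2 | new therapy | no | yes |
| 6.1 column header | treatment discontinued | yes | yes |

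The rules disagree for both subjects. For U, only the header opens survival contact, and it carries the footnote that restricts it.

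**Step 2. Look for another route for U.** Under 7.1.2.6.3 required imaging ends, because PD is documented. Under 7.1.5.3.3 imaging may continue, if unconfirmed PD counts as unverified. The two sections conflict for this subject. Disease-status follow-up in 7.1.5.3.2 runs only until progression, which has already occurred. At the 90-day contact the flowchart marks adverse event reporting only; survival status is marked only in the survival column. The remaining routes are a discretionary confirming scan, new therapy, or the optional Sponsor check.

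**Step 3. Size, by illustration.** The plan has no OS figure to reproduce. Every clinical input below is an assumption.

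*Set A.* Median time to PD 2.5 months; median survival after PD 2 months if unstable and 8 months otherwise; exponential times; no unstable subject starts new therapy. With PD rate a and post-PD rate b, S(t) = (b e^(−at) − a e^(−bt)) / (b − a). In units of ln 2 per month, a = 1/2.5 = 0.4, and b = 1/2 = 0.5 (unstable) or 1/8 = 0.125 (other). At 12 months the exponential terms are 2^(−4.8) = 0.0359, 2^(−6) = 0.0156 and 2^(−1.5) = 0.3536.

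- Unstable: (0.5 × 0.0359 − 0.4 × 0.0156) / 0.1 = 0.117
- Other: (0.125 × 0.0359 − 0.4 × 0.3536) / (−0.275) = 0.498
- 30% unstable: 0.3 × 0.117 + 0.7 × 0.498 = 0.384, against 0.383 by simulation

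Simulated Kaplan-Meier OS at 12 months (400,000 subjects):

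| Unstable share | True | Deaths known to Day 90 after stopping | Censored at stopping |
|---|---|---|---|
| 20% | 0.420 | 0.450 (+3.0 points) | 0.516 (+9.6) |
| 30% | 0.383 | 0.426 (+4.3) | 0.529 (+14.6) |
| 40% | 0.346 | 0.403 (+5.7) | 0.547 (+20.1) |

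At 30% unstable, median OS is 9.2, 10.1 and 12.7 months respectively.

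*Set B.* Median time to PD 3 months; post-PD median 8 months (stable) and 2 or 4 months (unstable); unstable share 10% to 30%; 0% or 50% of unstable subjects entering through new therapy; last contact at stopping or 3 months later; 200,000 subjects per scenario.

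| Scenario | True | Known to 3 months | Censored at stopping |
|---|---|---|---|
| 10% unstable, 4-month median, half on new therapy | 0.505 | 0.512 (+0.7) | 0.521 (+1.6) |
| 30%, 4-month median, none on new therapy | 0.463 | 0.507 (+4.4) | 0.566 (+10.3) |
| 30%, 2-month median, none on new therapy | 0.416 | 0.459 (+4.3) | 0.566 (+15.0) |

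Across Set B, median OS rises by 0.2 to 1.1 months with contact to 3 months and by 0.4 to 3.7 months with censoring at stopping. Over both sets the 12-month overstatement is 0.7 to 5.7 points in the first case and 1.6 to 20.1 in the second.

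**The case against.** A reader might infer that these subjects never enter survival follow-up. The documents do not support that. Section 5.8.1 keeps subjects in the trial after treatment stops and asks for the flowchart procedures to be completed, and the flowchart header times survival calls from discontinuation. A site working from the header would call subject U. Section 7.1.5.3.3 can be read as keeping U in imaging follow-up until death. A discretionary scan may confirm PD. The optional Sponsor check is tied, as an example, to interim and final analyses and covers all subjects not known to have died. Nor is new therapy a trigger in one place only; two sections have it.

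A reader might also infer that OS is overstated as a matter of fact. That is not established either. No OS censoring rule appears in these documents, the share of such subjects is unknown, and OS is exploratory in a trial without hypothesis testing (8.7). No between-arm OS comparison is specified, so a difference in bias between arms would matter little. Exemption from SAE reporting does not mean that a death date goes unrecorded. The largest figures assume that nothing is learned after stopping, although adverse events are monitored for up to 90 days. With a 2-month post-PD median, 1 − 2^(−2.96/2) = 64% of unstable subjects would have died by Day 90.

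All of this limits the size and certainty of the bias. It does not settle which entry rule applies. The header conflicts with its own footnote, Section 5.8.1 refers back to the sections that hold the narrow triggers, 7.1.5.3.3 conflicts with 7.1.2.6.3, and the Sponsor check is optional.

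**Conclusion.** The point holds as an inconsistency with a conditional consequence. The entry rules conflict, and under the text triggers an unstable subject with unconfirmed PD has no scheduled route into survival contact without a discretionary scan, new therapy or an optional Sponsor request. If the footnotes are followed as written, the subjects lost are likely to be those with the poorest prognosis, and exploratory OS may be biased upward.

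The direction follows from that prognosis assumption and was upward in every scenario run. The size rests wholly on assumed inputs: roughly 1 to 6 points on 12-month OS if deaths are known to Day 90, about 2 to 20 points if subjects are censored at stopping, and close to zero if sites follow the header or the Sponsor makes the check. The primary safety endpoint and ORR do not depend on survival contact. The correction is worth making because it is cheap and missed death dates may not be recoverable.

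**What to change.** Reconcile Section 2.1, footnotes 11 and 12 and the survival column header in 6.1, and Sections 7.1.1.6.2, 7.1.5.3.3 and 7.1.5.3.4 to one rule. Every subject who is off treatment and no longer in scheduled imaging, for any reason (PD confirmed or not, clinical progression, or new anticancer therapy), enters 12-weekly survival contact until death, withdrawal of consent, loss to follow-up or end of study. Record the date of death for all subjects, including deaths from progression that fall outside SAE reporting. Align 7.1.2.6.3 with 7.1.5.3.3, so that it is clear when imaging ends for a subject with unconfirmed PD. State the OS censoring rule in the supplemental SAP.

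The cost is protocol wording and a few extra telephone calls per affected subject. No new visits, procedures or subjects are needed.

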## **7.0 TRIAL PROCEDURES**

### **7.1 Trial Procedures**

The Trial Flow Chart - Section 6.0 summarizes the trial procedures to be performed at each visit. Individual trial procedures are described in detail below. It may be necessary to perform these procedures at unscheduled time points if deemed clinically necessary by the investigator.

Furthermore, additional evaluations/testing may be deemed necessary by the investigator and or the Sponsor for reasons related to subject safety. In some cases, such evaluation/testing may be potentially sensitive in nature (e.g., HIV, Hepatitis C, etc.), and thus local regulations may require that additional informed consent be obtained from the subject. In these cases, such evaluations/testing will be performed in accordance with those regulations.

